3.6 Procedures to Minimize Potential Risks

Drug infusions will be administered in the Washington University Clinical Research Unit under the supervision of the PI and the co-investigators. Subjects will be monitored by study personnel during infusions, and dedicated RN personnel is available 24-hours a day on site.

Inclusion and exclusion criteria, monitoring, and the clinical protocol are designed to ensure that risks are absolutely minimal. Participants are informed that participation is voluntary and they may refuse to participate and may withdraw from the study at any time without penalty. A pregnancy test will be performed on women of childbearing potential and subjects excluded if pregnant. Subjects will be told that in the event of a physical injury as the direct result of study procedures, they will be cared for by a member of the investigating team at no cost, within the limits of the Washington University compensation plan.

Subjects will be instructed at the beginning of the visit that they can alert the investigator any time they experience bothersome side effects. In particular, they will be instructed to immediately report palpitations or dizziness/lightheadedness. Continuous physiologic monitoring (ECG, pulse oximetry, and intermittent non-invasive blood pressure) will be used from the beginning of drug infusion until 2 hours after ondansetron infusion is complete. Medical personnel will be immediately available throughout the visit. The subject can voluntarily withdraw from the study at any time.

With regard to confidentiality; 1) all subjects will be assigned a study ID number, 2) Samples will be kept

confidentially. They will be coded, with a key to the code linking code numbers to names kept at a separate location, under lock and key. 3) The link to identifiers will be destroyed at the end of the study. 4) Data will be stored under lock and key (office, file cabinet) and only the investigators and research team will have access. If data are published, there will be no link to identifiers. Study data will not be revealed to any organization, individuals other than the subjects, or the subjects themselves. 5) Study data will not be entered in subjects' medical records.

3.6.1 Prevention, diagnosis and management of ondansetron-associated arrhythmia

To minimize the risk of ondansetron-associated arrhythmia, subjects will have a 12-lead ECG performed at the screening visit. Subjects with QTc>450msec or any arrhythmia will be excluded. Potential subjects that would be at elevated risk of developing ondansetron-associated arrhythmia (e.g., current use of QT-prolonging medication) are ineligible for this study. The ondansetron dose used (16mg IV infused over 15min) is approved and commonly used with chemotherapy. Subjects will be monitored with telemetry from the beginning of drug infusion until 2 hrs after infusion is complete. If arrhythmias or prolonged QT develop at any time during the study, subjects will be immediately assessed by a physician. If ECG abnormalities are mild (e.g., infrequent premature atrial/ventricular contractions or QTc>450ms but <500ms), subjects will be monitored in the pain management center by nursing and medical personnel for at least 4 hrs. If the signs/symptoms meet the severity criteria described in Section 3.2 ("Premature discontinuation of protocol for a single patient"), the patient will be withdrawn from the study and sent to the Barnes-Jewish Hospital emergency department (ED) for further evaluation, including cardiology consultation or hospital admission, as needed.

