3.2 Dose Limiting Toxicities

The dose-limiting toxicities (DLT) for the study are defined as follows:

- New QTc prolongation >60ms greater than baseline, or QTc>450ms
- Troponin T elevation > 0.03 ng/mL
- Syncope
- Sustained increase or decrease in SBP of >30 mmHg systolic or >20 mmHg diastolic
- Sustained vital sign abnormalities
 - HR<40 or >120 beats per minute
 - SpO2 <92%

- ALT/AST \geq 3xULN AND total bilirubin \geq 2xULN
- AST/ALT \geq 8xULN
- Altered mental status (delirium, inability to follow simple commands)
- Persistent visual disturbances

If DLT is observed in >2 participants, ondansetron dose will be reduced to 12 mg for all new participants.

If further DLT is observed in >2 participants receiving 12 mg ondansetron, the dose will be reduced to 8 mg for all new participants.

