3.3 Premature withdrawal from a study for a single patient

If at any time the constraints of this protocol are considered to be detrimental to the patient's health and/or the patient no longer wishes to continue protocol therapy, the participant will be withdrawn from the study and the reason(s) for withdrawal documented in the case report forms.

Any participant will be withdrawn from the study in the following scenarios:

- Death
- Anaphylaxis
- Allergic reaction with urticarial, rash or dyspnea,
- Cardiac arrest
- Atrial or ventricular fibrillation
- Ventricular Tachycardia
- Syncope
- AV block (2nd degree type II or 3rd degree)
- New QTc prolongation >60ms greater than baseline or >470ms for men or >480ms for women
- Troponin elevation > 0.03 ng/mL
- Sustained increase or decrease in SBP of >30 mmHg systolic or >20 mmHg diastolic
- Sustained vital sign abnormalities
 - HR<40 or >120 beats per minute
 - SpO₂ <92%
 - Temperature <36 C or >38°C
- ALT/AST \geq 3xULN AND total bilirubin \geq 2xULN
- AST/ALT \geq 8xULN
- Thrombocytopenia
- Clinically meaningful CBC abnormalities (compared to baseline)
- Altered mental status (delirium, inability to follow simple commands)
- Seizures
- Persistent visual disturbances
- General or specific changes in the patient's condition that render the patient unable to receive further treatment in the judgment of the investigator
- Suspected or confirmed pregnancy
- Serious non-compliance with the study protocol
- Lost to follow-up
- Patient withdraws consent
- Investigator removes the patient from study
- Investigator decides to close the study

If a participant withdraws from the study, the participant will be replaced in order to provide the required number of evaluable subjects. Subjects will be withdrawn if the investigator decides that discontinuation is in the best interest of the subject, or the subject requests withdrawal from the study.

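### Section 3.6.1 labels as mild some QTc readings for which 3.3 requires withdrawal, and its emergency-transfer sentence cites the wrong section, so the level of care for those readings is unclear

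*Combined protocol and SAP*

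**What the plan says.** Three sections of the combined protocol and SAP set post-infusion QTc limits.

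- **Section 3.6.1** (ondansetron-associated arrhythmia) has any arrhythmia or QT prolongation assessed by a physician at once, then grades the response. The lower grade begins "If ECG abnormalities are mild (e.g., infrequent premature atrial/ventricular contractions or QTc>450ms but <500ms", and for it "subjects will be monitored in the pain management center by nursing and medical personnel for at least 4 hrs". The higher grade follows in the next sentence, which opens "If the signs/symptoms meet the severity criteria described in Section 3.2" and gives that section the title "Premature discontinuation of protocol for a single patient". The action it then sets is that "the patient will be withdrawn from the study and sent to the Barnes-Jewish Hospital emergency department (ED) for further evaluation".
- **Section 3.3** lists the events for which any participant is withdrawn. Its QTc entry is "New QTc prolongation >60ms greater than baseline or >470ms for men or >480ms for women".
- **Section 3.2** is the dose-limiting toxicity (DLT) list. Its QTc entry is "New QTc prolongation >60ms greater than baseline, or QTc>450ms". It governs dose reduction for later participants and sets no action for the individual who had the event.

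A QTc of 450 ms is also the entry limit (2.3.3) and the limit for giving the second infusion (2.4.3).

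**The concern.** Section 3.6.1 is where staff would look when a post-infusion ECG shows a long QTc. The range it calls mild has no sex-specific upper limit and no limit on change from baseline, whereas 3.3 has both. Part of the range is therefore observed locally under one sentence and sent to the emergency department under the next.

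The sentence that should settle the matter has a faulty reference. Its number leads to the DLT list and its title leads to 3.3, and the two have different absolute QTc limits.

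At stake is the safety handling of a recognised cardiac risk of ondansetron (3.5.4). A 12-lead ECG that could produce such a reading is planned before discharge in every session (2.4.3).

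**Working it through.** No power or sample-size figure is involved. The check compares thresholds in whole milliseconds.

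**Inputs**
- Mild (3.6.1): 451 to 499 ms, both sexes, which is 499 − 451 + 1 = 49 values.
- Withdrawal (3.3): reading − baseline > 60 ms, or reading > 470 ms (men) or > 480 ms (women).
- DLT (3.2): reading − baseline > 60 ms, or reading > 450 ms.
- Highest eligible baseline (2.3.3): 450 ms.

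**Step 1: readings that are both mild and a reason for withdrawal**
- Men, any baseline: 471–499 ms, or 499 − 471 + 1 = 29 of 49 values.
- Women, any baseline: 481–499 ms, or 499 − 481 + 1 = 19 of 49 values.
- Either sex, through the change limit: readings of 451–499 ms that are at least 61 ms above baseline. This needs a baseline of 499 − 61 = 438 ms or less. It adds to the sex-specific ranges only below 410 ms (men) or 420 ms (women).

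| Baseline (ms) | Men | Women |
|---|---|---|
| 450 | 471–499 (29) | 481–499 (19) |
| 420 | 471–499 (29) | 481–499 (19) |
| 410 | 471–499 (29) | 471–499 (29) |
| 400 | 461–499 (39) | 461–499 (39) |
| 390 or lower | 451–499 (49) | 451–499 (49) |

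These counts show how far the two rules overlap. They say nothing about how often the readings will occur.

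**Step 2: smallest rise that reaches the overlap**
- From 450 ms: 471 − 450 = 21 ms (men), 481 − 450 = 31 ms (women).
- From 420 ms: 51 ms (men), 61 ms (women).
- From 390 to 410 ms: 61 ms in both.

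**Step 3: the emergency-transfer trigger under each reading of the reference**
- By title (3.3): above 470 ms (men), above 480 ms (women), or a rise above 60 ms.
- By number (3.2): above 450 ms or a rise above 60 ms, so the whole mild range would qualify.
- The two differ at 451–470 ms (men) and 451–480 ms (women) when the rise is 60 ms or less.

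**Step 4: the proposed range**
Define mild as above 450 ms, up to 470 ms (men) or 480 ms (women), with a rise of at most 60 ms. Above 450 ms this is the exact complement of the 3.3 rule, so no reading has two instructions and none has no instruction. The change limit is needed: with an upper cut at 470/480 ms alone, a baseline of 400 ms would leave 461–470 ms (10 values, men) and 461–480 ms (20 values, women) in both groups.

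**The case against.** The strongest reply is that the two sentences in 3.6.1 are graded. The QTc range is only an example, and the second sentence reads naturally as escalation for anyone who meets the withdrawal criteria. The title it gives resembles the heading of 3.3 and nothing in 3.2, so few readers would send every reading of 451 ms to the emergency department just after being told it is mild. This has force, and it is the likely intent. But the example states an explicit upper limit of 500 ms that extends into the 3.3 criteria, and the sentence meant to override it cites a section with a different QTc limit. The synopsis uses the number 3.2 correctly, for dose reduction, so a reader has some reason to trust it.

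A reader might infer more: that the mild label decides whether a man at 475 ms in the first session stays in and gives paired data, or whether he counts toward stopping. The documents do not support that. The mild sentence says where and for how long a participant is watched; it does not say that he continues. Section 3.3 is mandatory, and its replacement rule ("If a participant withdraws from the study, the participant will be replaced in order to provide the required number of evaluable subjects") follows from withdrawal. Section 3.4 counts those who meet the withdrawal criteria because of adverse effects, whatever 3.6.1 calls the reading.

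Two safeguards also stand. Physician assessment is immediate in every case, and the ECG is repeated before the second infusion, with withdrawal if QTc exceeds 450 ms.

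**Conclusion.** The point holds as a limited inconsistency in safety handling. For 471–499 ms in men, 481–499 ms in women, and 451–499 ms after a rise of more than 60 ms, the level of care in 3.6.1 is contradictory if its mild range is applied. The trigger for emergency transfer also depends on whether the cited number or the cited title is followed. Study status, replacement, evaluability, the stopping count and the analysis are unaffected.

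How often this would arise cannot be derived from the documents. It is probably uncommon. Mean QTc changes in the first 8 participants of the earlier human study were −2.5 ms (SD 16.1) with tariquidar and 2.9 ms (SD 13.1) without (2.2), and 3.5.4 cites a maximum prolongation of 20 ms at 32 mg. That evidence is thin, since only 2 of those 8 received 16 mg.

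Two other inferences should be avoided. The mismatched title suggests that the sections were renumbered, but the documents do not say so. The 450 ms limit in the DLT list is not itself at fault, because it serves a different purpose from the withdrawal limits.

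**What to change.** Make two changes in Section 3.6.1.

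1. Correct the reference so that it cites Section 3.3 by its present heading (Premature withdrawal from a study for a single patient).
2. Replace the QTc example in the mild sentence with: QTc above 450 ms and up to 470 ms (men) or 480 ms (women), with a rise of no more than 60 ms from baseline. Add that readings beyond this follow Section 3.3 and go to the emergency department.

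Leave the limits in 2.3.3, 2.4.3, 3.2 and 3.3 as they are. The change follows the title and not the number in the present reference, and the sponsor should confirm that this is the intended trigger.

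The cost is a short wording amendment. It needs no new measurement and does not affect sample size or blinding.

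### Section 3.6.1 treats QTc above 450 and below 500 ms as mild and monitored on site, yet part of that range means withdrawal under 3.3 and emergency-department referral under 3.6.1 itself, and the linking reference is inconsistent

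*Combined protocol and SAP*

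**What the plan says.** Four sections of the combined protocol and SAP set rules on QTc.

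- **Section 3.6.1** applies whenever an arrhythmia or prolonged QT develops during the study, and starts with immediate assessment by a physician. It then defines a lower tier by example: "If ECG abnormalities are mild (e.g., infrequent premature atrial/ventricular contractions or QTc>450ms but <500ms". The same sentence runs on to the action for that tier: "QTc>450ms but <500ms), subjects will be monitored in the pain management center by nursing and medical personnel for at least 4 hrs". The next sentence defines an upper tier: "If the signs/symptoms meet the severity criteria described in Section 3.2", with the section title given as "Premature discontinuation of protocol for a single patient", then "the patient will be withdrawn from the study and sent to the Barnes-Jewish Hospital emergency department (ED) for further evaluation".
- **Section 3.3**, headed "Premature withdrawal from a study for a single patient", opens its list with "Any participant will be withdrawn from the study in the following scenarios". Its QTc entry is "New QTc prolongation >60ms greater than baseline or >470ms for men or >480ms for women".
- **Section 3.2** is the list of dose-limiting toxicities. Its QTc entry is a rise of more than 60 ms or a value above 450 ms. The stated consequence is a lower ondansetron dose for new participants once more than 2 participants are affected. It contains no rule for withdrawing an individual.
- **Section 2.4.3** repeats the 12-lead ECG before the second infusion. A participant above 450 ms at that point does not receive the second dose and is withdrawn.

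**The concern.** The mild QTc range in 3.6.1 is the same for both sexes and carries no condition on change from baseline. The withdrawal rule in 3.3 has both, and its limits fall inside that range. One ECG can therefore be classed as mild and observed on site, and also require withdrawal and transfer to the emergency department. Nothing in 3.6.1 says that the mild tier stops where 3.3 begins.

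The reference that should separate the two tiers does not do so cleanly. Followed by number it leads to one QTc limit, and followed by title to another. These are instructions that staff act on soon after dosing, in a trial where tolerability is a primary objective, so the disposition should not depend on which sentence or which half of a reference a reader follows.

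**Working it through.** There is no sample-size or power figure to reproduce. The check compares QTc limits and then tests the reference against the section headings.

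**Step 1: absolute limits.** The mild range in 3.6.1 is above 450 and below 500 ms. Section 3.3 withdraws men above 470 ms and women above 480 ms. The overlap is above 470 to below 500 ms in men and above 480 to below 500 ms in women.

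**Step 2: the rise rule.** Below those absolute limits, a value Q still meets 3.3 if Q − baseline > 60, that is, if baseline < Q − 60.

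- Men, Q from just above 450 up to 470 ms: baseline below 390 (450 − 60) up to below 410 (470 − 60).
- Women, Q from just above 450 up to 480 ms: baseline below 390 up to below 420 (480 − 60).
- At a baseline of 400 ms, withdrawal starts above 460 ms. At 390 ms or lower, every value in the mild range meets 3.3.

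The exclusion criteria in 2.3.3 bar only QTc above 450 ms, so such baselines are eligible.

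**Step 3: test cases.**

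| Case | Mild example in 3.6.1 | Withdrawal under 3.3 | Listed in 3.2 |
|---|---|---|---|
| Man at 485 ms | Yes | Yes (above 470) | Yes |
| Either sex, 390 to 455 ms | Yes | Yes (455 − 390 = 65, above 60) | Yes |
| Either sex, 420 to 460 ms | Yes | No (rise 40) | Yes |
| Woman, 430 to 475 ms | Yes | No (rise 45, not above 480) | Yes |

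The first two rows fall under both instructions in 3.6.1 once the criteria are taken from 3.3. The last two show where 3.6.1 and 3.3 agree: men above 450 to 470 ms and women above 450 to 480 ms, with a rise of 60 ms or less.

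**Step 4: the reference.** The number is 3.2, but the title is close to the 3.3 heading, though not identical, and bears no relation to the 3.2 heading. Read by title, the last two rows stay in the monitoring tier. Read by number, all four rows meet the criteria, because 3.2 lists any value above 450 ms, and no QTc value is left for monitoring alone.

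**Step 5: the pre-infusion rule.** Section 3.6.1 applies at any time during the study, so it also covers the ECG before the second infusion. A participant at 460 ms there, with a rise of 60 ms or less, is a mild example under 3.6.1, is not withdrawn by the QTc entry in 3.3, and is withdrawn by 2.4.3. That section does not state a location of care for this case.

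**The case against.** The strongest answer is that 3.6.1 is a sequence: assess, observe if mild, escalate if the criteria are met. The QTc range is only an example, 3.6.1 does not say that observed participants remain in the study, and 3.3 is mandatory. On that reading a man at 485 ms is assessed, withdrawn and referred. This reading is possible and it narrows the point, since observation and withdrawal do not exclude each other. It does not remove the point: a single reading of 485 ms satisfies both conditions at once, the text states no exception or priority, and the label and the location of care still differ.

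It can also be said that anyone turning to 3.2 would see the wrong heading, and that the by-number reading empties the mild tier of QTc values and so defeats itself. That makes 3.3 the likely target, but the printed number still leads to a different disposition.

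Several stronger readings are tempting, and the documents do not support them.

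- *That 3.6.1 tells staff to keep a man at 485 ms in the study.* It is silent on continuation.
- *That the trial will lose paired data.* This follows only from the by-number reading and only in session 1, where a participant whom 3.3 would keep is withdrawn before the second session. Even then, 2.4.3 would have to allow the second infusion. After session 2 both infusions have been given, so withdrawal at that point need not lose the pair or require replacement.
- *That the number of scheduled discharge ECGs, or the share of the 50 ms range that overlaps, measures the problem.* The rule applies throughout the study, with telemetry and an ECG before the second infusion, and the width of a range is not a frequency.
- *That a dose-limiting-toxicity limit below the withdrawal limit is itself an error.* The two limits have different stated consequences.

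**Conclusion.** The inconsistency is real and limited. Sections 3.6.1 and 3.3 give the same QTc result two labels and two locations of care in men above 470 ms, in women above 480 ms, and in either sex after a rise of more than 60 ms, within the range above 450 and below 500 ms. The trigger for withdrawal in 3.6.1 carries a number and a title that lead to different lists, and 2.4.3 adds a third rule at a specific time point.

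The conclusion rests only on the text. It assumes that the 3.6.1 sentence was meant to point to 3.3, which its title supports. How many participants would be affected cannot be estimated, because no baseline QTc distribution is given. No effect on the pharmacokinetic comparison or the sample size is shown. The point deserves correction because it concerns an operative safety rule and costs little to repair.

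**What to change.** Reconcile 2.4.3, 3.2, 3.3 and 3.6.1 so that each QTc value or change, at each time point, leads to one stated disposition and one stated location of care. If observation is meant as a step before escalation, 3.6.1 should say so and state which instruction prevails when both conditions are met. Make the number and title of the reference in 3.6.1 agree. The clinical team chooses all limits and actions; this review takes no position on them.

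As a separate clerical correction, section 3.5.2 points to 3.4 for managing lumbar-puncture complications. Section 3.4 covers premature termination of the study; that management is in 3.6.2 and 3.6.4.

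The cost is one wording amendment, with no added procedures or participants.

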3.6.2 Prevention, diagnosis and management of post-lumbar puncture headache (PLPH)

Lumbar puncture and sampling procedure will conducted in a way to minimize the effect of risk factors contributing PLPH development. Particularly, an atraumatic needle of 25 G diameter will be used for LP procedure. Passive withdrawal of CSF is known as associated with a lower risk for headache, therefore active withdraw with syringe will be avoided left only for rare cases.

Subjects will be asked to notify clinical personnel immediately if they develop a headache while in the clinical research unit. Additionally, the periodic nursing assessment (see supplementary document) will include questions about headache. If a participant endorses new-onset headache, the anesthesiologist will be notified. The anesthesiologist will perform a brief history and physical exam to determine whether or not the symptoms suggest PLPH. If PLPH is likely and symptoms are mild, conservative treatment will be initiated. The participant will be encouraged to lie in a comfortable position and drink fluids. The subject will also be offered analgesics including acetaminophen/butalbital/caffeine (e.g. Fioricet®), ibuprofen, or acetaminophen alone. IV fluids or medication will be reserved for subjects who cannot tolerate oral administration due to nausea/vomiting. If symptoms are severe (e.g. uncontrollable nausea/vomiting, severe subject distress), the subject will be removed from the study and epidural blood patch will be offered (procedure described below).

Discharge paperwork will include clear descriptions of PLPH and instructions about whom to contact in the case of headache. If a subject reports likely PLPH by contacting study personnel or during a follow-up phone call, symptom severity will be assessed. Conservative treatment (as described above) will be offered for the first 24-48 hrs. If unresolved, the participants will be brought to the Clinical Research Unit for further evaluation or treatment per discretion of the investigators which could include a potential epidural blood patch procedures, performed by the anesthesiologists on the study team.

Epidural blood patches are commonly performed by our Acute Pain Service. Sterile technique (including chlorhexidine swabs, caps, masks, and sterile gloves) is used at all steps by all personnel involved. First, the epidural space is located using a standard Tuohy needle and loss-of-resistance technique. Next, 20ml of the subject's blood is drawn and then injected through the Tuohy needle. Injection is stopped if the subject complains of pressure or paresthesia that could indicate compression of the cauda equina.

3.6.3 Prevention of drug-drug interactions between study drugs and concomitantly used antidepressants

Citalopram, Escitalopram and Duloxetine are not known to produce clinically meaningful interactions when combined with potent P-gp or CYP3A4 inhibitors. When tested specifically in combination with P-gp inhibitors such

as simeprevir, cyclosporine, and verapamil, meaningful interactions were NOT identified for escitalopram and duloxetine⁴⁴⁻⁴⁶. Given that tariquidar is a selective P-gp inhibitor (and possibly weak CYP3A4 inhibitor), we do not expect any meaningful interactions with citalopram, escitalopram, or duloxetine.

Table 3 outlines the potential of drug interactions between SSRI/SNRI antidepressants in the context of use with P-gp inhibitors, and served as a basis for inclusion/exclusion of particular SSRI/SNRI antidepressants.

Table 3. Potential of drug interactions between SSRI/SNRI antidepressants and P-gp inhibitors.

SSRI	FDA-approved maximum dose (mg/day)	Known P-gp substrate	Known CYP3A4 substrate	Known / Clinically relevant interactions with other P-gp inhibitors	Clinically-relevant interactions with CYP3A4 inhibitors	Comments on QT interval prolongation
Citalopram	40	No ^{47,48}	Yes, CYP3A4 and CYP2C19 ⁴⁹	None found (extensive search in PubMed, Lexi-Comp, and IBM Micromedex)	No. ketoconazole co-administration did not significantly affect the pharmacokinetics of citalopram [1]	Dose-dependent QT prolongation ^{47,50}
Escitalopram	20	No ^{48,51}	Yes, CYP3A4, CYP2D6, and CYP2C19	None found (extensive search in PubMed, Lexi-Comp, and IBM Micromedex) ⁴⁹	No. Administration of ritonavir (potent CYP3A4 inhibitor) did not affect the pharmacokinetics of Escitalopram ⁵²	No clinically relevant QT prolongation vs placebo ⁵²
Paroxetine	60	Possibly ^{53,54} . However, may be a weak inhibitor of P-gp ⁵⁵	No. CYP2D6 and unchanged excretion to urine	No	No. Also, paroxetine does not meaningfully inhibit CYP3A4 ⁵⁶	Likely rare, only a few cases reported ⁵⁷
Fluoxetine	80	Conflicting data ^{53,54,58}	Yes. Also possible inhibitor of CYP 3A4. Although overall CYP3A4 inhibition with fluoxetine is likely not clinically meaningful ⁴⁴ , some potential interactions have been reported with CYP3A4 substrates. ⁵⁹	No	Verapamil (likely due to Fluoxetine's inhibition of verapamil metabolism ⁴⁴)	Fluoxetine has been associated with potential increase in risk of QT interval prolongation ⁵⁰

Sertraline	200	No ^{60,61} . However, may be a weak inhibitor of P-gp ⁵⁵	Unclear. Multiple sources of data suggest 1 st pass metabolism and N-demethylation, but specific enzymes are not well understood ^{60,61} , possibly suggesting CYP2C19 and CYP2B6	None found (extensive search in PubMed, Lexi-Comp, and IBM Micromedex)	No	Likely not significant ⁶²
SNRI	FDA-approved maximum dose (mg/day)	Known P-gp substrate	Known CYP3A4 substrate	Known / Clinically relevant interactions with other P-gp inhibitors	Clinically-relevant interactions with CYP3A4 inhibitors	Comments on QT interval prolongation
Duloxetine	120	No ^{63,58}	No. Metabolized primarily by CYP1A2 and CYP2D6	None found (extensive search in PubMed, Lexi-Comp, and IBM Micromedex) ⁴⁹	None found	No clinically relevant QT prolongation vs placebo ⁶³
Venlafaxine	225	Possibly ^{53,54}	Yes. Also metabolized by CYP2D6 (major). Venlafaxine does not meaningfully inhibit CYP3A4 ⁶⁴	Interaction with ketoconazole, likely due to CYP3A4 rather than P-gp inhibition. Minimum interference with P-gp activity in vitro ⁶⁴	Clinically meaningful interaction with ketoconazole, likely because 3A4 inhibition ⁴⁶	QT prolongation rare, likely happens only with very high doses / overdose ^{65,66}
Desvenlafaxine	400mg, but doses >50mg not recommended	No ⁶⁷	Yes (minor). Also excreted renally unchanged (45%). Desvenlafaxine does not meaningfully inhibit CYP3A4 ⁶⁴	Unlikely to be affected ⁶⁷	Ketoconazole can increase plasma concentrations of desvenlafaxine. Potential interaction with potent CYP3A4 inhibitors.	No clinically relevant QT prolongation vs placebo ⁶⁷

For patient safety, we will limit maximally allowable doses of **citalopram**, **escitalopram** and **duloxetine** in enrolled participants to 50% of FDA-approved maximum dose, eg, 20mg for citalopram, 10mg for escitalopram and 60mg for duloxetine.

Due to possible interactions with other SSRI/SNRI medication, we will exclude patients taking other SSRI/SNRI medications such as paroxetine, fluoxetine, sertraline, venlafaxine, and desvenlafaxine.

